(5-b) to evaluate whether the investigational device with Speech enhancer activated provides better subjective speech intelligibility and less listening effort than without speech enhancer for distant speech in a quiet situation with access to visual cues for people with moderate to severe hearing loss. Tested null hypothesis: there is no difference between Speech Enhancer activated or not with the subjective assessment questionnaire.

(5-c) to evaluate whether the investigational device with Speech enhancer activated provides better subjective speech intelligibility and less listening effort than without speech enhancer for speech from an adjacent room a quiet situation without access to visual cues for people with moderate to severe hearing loss. Tested null hypothesis: there is no difference between Speech Enhancer activated or not with the subjective assessment questionnaire. Secondary objectives for the Hearing aid benefit part are:

3 Identification and description of the investigational device

In this clinical investigation, the investigational device will be used according to its intended use. The intended use of the hearing aid is to amplify and transmit sound to the ear and thereby compensate for impaired hearing.

4 Design of the clinical investigation

This clinical investigation is an interventional study, executed at one investigation site, with a confirmatory design. The investigation model is single group, with a randomized test order where the test conditions are fully crossed-over. It is a single blinded study because all test conditions are implemented in the same hearing aid, so that the tested condition cannot be identified by the test participant.

The tested conditions for the primary and secondary objectives are programmed in the investigational device, the CE marked Phonak Audeo P-90-R. The tested features can be activated via the MyPhonak APP by the subjects/investigator.

5 Risks and benefits of the investigational device and clinical Investigation

The product-related risks and the clinical investigation procedure-related risks are well controlled during the clinical investigation as the participant will always be under the supervision of the investigator. Even if the residual risk probabilities range from remote (1:100'000 – 1:1'000'000) to incredible (< 1:10.000.000), any adverse effect will be recorded, reported and monitored during the clinical investigation.

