9.1 Determination of Sample Size

a. Introduction and background

The sample size is computed on the primary outcome: SRTs measured in a 2 by 2 factorial design:

- 2 different test setups, talker from the side vs. from the back,
- 2 test conditions, R-BF vs. I-BF.

Traditional power analysis packages or software are unable to compute sample size calculation analytically for a two-way repeated measures design. Green & MacLeod (2016) and Kumle et al. (2021) propose an alternative power analysis based on simulations for a generalized (linear) mixed-effect model.

Mixed-effect models should be preferred over analysis of variance (Oleson et al., 2019) as it makes no assumption about the distribution of the outcome variable (only residuals should be independent and identically distributed) or sphericity (correlation between repeated measures) and allows to include random slopes in the model, assuming the fixed effects are not constant across tested subjects.

b. Principle of power analysis based on simulation

The principle for simulation-based power analysis is to 1) simulate a new dataset, 2) analysis each set and test for significance, and 3) calculate the proportion of significant to all simulations. The simulation of new data set is not trivial as it will affect the accuracy of the simulation. One possible way to generate the new data-set is to use an existing data-set from a well powered study. The power will be computed based on the reference data set in order to detect an a priori determined fixed effect, also described as the smallest effect size of interest (SESOI).

c. Reference data set

The reference data set is taken from Latzel & Appelton (2015) who measured SRTs with different beamformers (including the R-Bf and the I-BF) and 2 test setups with different spatial configurations (noise from around vs side). Individual data from this reference study are available and show interesting properties, as the experiment was conducted on 20 hearing aid users with the same range of hearing loss degree (moderate to severe) at the same investigation site. While these test setups have always the talker in front, these data provide valuable information about within subject variance with hearing aid users. The reference analysis is based on a linear mixed-effect model is fitted with setup, device, and interactions as fixed effect and subject as random factor with device as

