random slope. The fixed effects are sum coded to get estimate of test setup and device that are easily interpreted.

The estimated effects are:

- test setup effect -0.6 dB SNR in average with a standard error of 0.2 dB SNR,
- device effect -3.0 dB SNR in average with a standard error of 0.4 dB SNR,
- interaction setup by device -1.6 dB SNR in average with a standard error of 0.4 dB SNR.

The effects of talker location and directional microphone are in line with data from Giuliani & Brayda (2019) who report SRTs measured with a single talker from different azimuth (from the back and the side) and different beamformers. While the test was performed with a different population (normal hearing listeners), different beamformers (virtual reality glasses) and test material (SRT in Italian with the Bocca test), the effects are similar with the reference data i.e., a decrease of 0.5 dB SNR when the talker is in the back instead of the side, a decrease of 4.5 dB SNR for the wider beamformer compared to narrower one, and a negative interaction of 0.5 dB SNR.

Results from both studies are consistent in direction even if there are some differences in their amplitudes. These observations are providing enough confidence for the simulation and we can therefore estimate the power based on the reference data for different sample sizes.

d. Simulation

We will make use of the mixed power function from the mixedpower package (Kumle et al., 2018, version 0.1.0) with varying sample size, since we want to compute the power for different sample sizes. The following simulation is based on 1000 runs with a varying sample size from 16 to 28. This range of sample sizes is usually reported in published articles about the effect of directional microphones and is also acceptable from a time and resources perspective.

Simulation is repeated two times. First on original data set where simulations rely on the same effect size provided by the reference model, which might be overpowered for the device effect. This increases the risk to perform analysis with inflated effect sizes and limit the chance of reproducing the results. The alternative is to specify the smallest effect size of interest (SESOI).

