Specifying SESOI makes “it possible to design studies which are worthwhile to run, as they have a predetermined power to detect an effect that is of interest” (Albers & Lakens, 2018; Kumle et al., 2021). However, prior knowledge is required to specify an effect size of interest. The SESOI for the test device will be set to 1 dB SNR difference between both tested conditions. The choice of this SESOI is based on a study review and experience from previous studies. The other SESOI are averaged between both reference studies i.e., -0.6 dB for the setup and -1.0 dB for the interaction.

e. Sample size

The power for different sample sizes is shown by fixed effect in following figure:

A sample size of 20 subjects might be sufficient to detect a difference of 1.0 dB SNR between both beamformer conditions with a power of 80%. The research question for the study focuses on the effect of the beamformer so that the decision is based on this main effect only. The sample size will be extended by 10 % to 22 participants as there is a risk of drop out during a clinical investigation with multiple visits over a longer time frame.

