9.3.2 Primary Endpoint Analysis

All the statistical tests will be performed at two-sided $\alpha=0.05$ if not specified differently. All reported p-values greater than or equal to 0.001 will be rounded to three decimal places and p-values less than 0.001 will be displayed as "<0.001". The analysis will be run using the statistical software R, version 4.1.1 (2021) (R Core Team 2021). The statistical analysis report will be written in a Rmarkdown format and exported into an HTML document.

a) Demographic Data

The following demographic and baseline characteristics will be tabulated overall for PP population: Age (years), 4-frequency Pure Tone Average (in dB HL), and case history i.e., hearing loss onset, otalgia, otorrhea, otitis, tinnitus.

For continuous variables (e.g., age) descriptive statistics will be presented (mean, interquartile range, and number of participants with data). For categorical variables frequencies, percentages and number of participants with data will be presented. The denominator for the percentages will be the number of patients with non-missing data.

b) Primary outcome: SRT for directional benefit

The SRT is a continuous variable expressed as the signal-to-noise ratio (in dB) necessary to achieve 50% intelligibility of the presented sentences. The SRT is measured in a 2 by 2 factorial design: talker factor (from the side or from the back) and beamformer (R-BF or I-BF). These SRTs will be analyzed with a linear mixed effect model with sequence (test-retest), talker location, beamformer, and interaction between location and beamformer as fixed effects. Participants will be treated as random factor with beamformer as random slope. The fixed effects are sum coded to get estimate of talker position and beamformer that are easily interpreted. The distribution of residuals will be visually checked to be independent and identically distributed. A likelihood ratio test will be made to obtain a p-value for each fixed effect.

c) Secondary outcome: listening effort for directional benefit

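### Fixed-effect p-values come from a likelihood ratio test with no reference distribution or fitting method named; under the usual chi-square reference the primary beamformer test has a size of about 5.9% at n=20 if the beamformer effect varies materially between participants

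*Combined protocol and SAP*

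**What the plan says.** Section 4 describes a study "executed at one investigation site, with a confirmatory design". Section 9.3.2 opens with "All the statistical tests will be performed at two-sided" alpha of 0.05. For the primary outcome, 9.3.2 b) fits a linear mixed model to the SRTs with sequence, talker location, beamformer and the location-by-beamformer interaction as fixed effects. On the random part it says: "Participants will be treated as random factor with beamformer as random slope". The p-values are then specified in one sentence: "A likelihood ratio test will be made to obtain a p-value for each fixed effect". Section 9.3.2 c) uses the same slope and the same sentence for listening effort. Section 9.3.2 f) also judges significance by a likelihood ratio test, with a subject random effect and a Bonferroni correction.

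No section states whether the statistic is referred to a chi-square, an F or t with a degrees-of-freedom method, or a bootstrap distribution, or whether the fit is ML or REML. The sample size in 9.1 e is tied to the beamformer effect, "so that the decision is based on this main effect only".

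**The concern.** A likelihood ratio test with a chi-square reference is a large-sample method. With a random beamformer slope, the beamformer effect is judged against variation between participants, which has only n-1 degrees of freedom: 19 for the 20 participants of the power calculation and 21 for the 22 recruited. Repeating the SRT eight times per participant does not add to these. The chi-square cut-off can then be too low, so that the primary test exceeds its stated 5%. Apart from its size, the gap leaves room for choice: different reference distributions can give different verdicts on the same data near p = 0.05, and this is the p-value that decides the primary objective.

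**Working it through.** **Inputs.** Two-sided alpha 0.05 (9.3.2). n = 20, extended by 10% to 22 (9.1 e; 20 x 1.10 = 22). Eight SRTs per participant: 2 beamformers x 2 locations x 2 sessions (section 6, item 1). Participants with missing data leave that analysis (9.3.7), so the data are taken as balanced. Reference study of 20 users: "device effect -3.0 dB SNR in average with a standard error of 0.4 dB SNR", setup SE 0.2, interaction SE 0.4 (9.1 c). The plan's 80% power cannot be reproduced, because it rests on individual data that the documents do not give.

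**Size when the slope variance is estimated above zero.** For balanced data and ML, the statistic is LR = n x log(1 + t^2/(n-1)), where t is the paired t on participant mean differences. Setting LR = 3.841 gives |t| = sqrt((n-1) x (exp(3.841/n) - 1)).

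- n = 20: sqrt(19 x (exp(3.841/20) - 1)) = 2.006, and 2 x P(t19 > 2.006) = 5.93%. An exact 5% test needs 2.093.
- n = 22: cut-off 2.002, size 5.84%.

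Direct ML fits of the planned model agreed with the closed form to within 0.000005 on the statistic.

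**Dependence on slope variation.** Let the ratio be the between-participant variance of the beamformer effect divided by the error variance of one participant's mean difference. When it is small, the slope variance is often estimated at zero and the size falls. Simulated sizes at n = 20 (1,000,000 null runs per cell; chi-square reference; the range covers correlated and uncorrelated intercept and slope; intercept variance assumed to be 5 times the error variance of one SRT):

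| Ratio | Size |
|---|---|
| 0 | 4.0-4.2% |
| 0.25 | 4.9-5.1% |
| 0.5 | 5.4-5.5% |
| 1 | 5.8% |
| 3 and above | 5.9% |

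**What the documents suggest about the ratio.** The reference model was "fitted with setup, device, and interactions as fixed effect and subject as random factor with device as" random slope, so only the device SE carries slope variance. For a balanced fit with two device levels (assumed), the ratio is (0.4/0.2)^2 - 1 = 3. If that study had one SRT per cell (assumed), this trial's retest halves the error variance and the ratio becomes 6. The SEs are rounded. With the retest the limits are 2 x ((0.35/0.25)^2 - 1) = 1.9 and 2 x ((0.45/0.15)^2 - 1) = 16. The lowest value without the retest is (0.35/0.25)^2 - 1 = 0.96.

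**Practical consequence at n = 20.** The verdict differs only for |t| between 2.006 and 2.093, that is, a paired-t p between 0.050 and 0.059. This covers 5.93% - 5.00% = about 0.9% of null trials. For a true 1.0 dB effect an SE is needed. From 9.1 c, with +/-0.5 coding (consistent with an interaction SE twice the setup SE): error variance 20 x 0.2^2 = 0.8, slope variance 20 x 0.4^2 - 0.8 = 2.4, and with the retest SE = sqrt((2.4 + 0.4)/20) = 0.374. Noncentral-t power is then 74.5% at 2.006 and 71.8% at 2.093, so about 2.8% of such trials change verdict.

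**Section 9.3.2 f), adjacent room.** Section 6, item 4 counts 14 assessments: 2 x (2 x 3 + 1). The adjacent room is the single last term, so it has two ratings per participant and attribute (Speech Enhancer on and off). With a subject random intercept the comparison again has n-1 degrees of freedom, and no slope variation is needed. At n = 20 with a chi-square reference the size is 5.9% to 7.0% at nominal 5%. The lower end applies when the two ratings are clearly correlated, the upper end when they are not. At 0.05/3 = 1.67% it is 2.1% to 2.7%, if Bonferroni covers the three attributes.

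**The case against.** The strongest reply is that nothing in the plan is contradictory. A likelihood ratio test is a recognised method, the chi-square reference and ML fit are supplied by this review, and a bootstrap reference would remove the excess with the test kept. That is fair, and is why the figures are conditional. But chi-square is the ordinary reading of an unqualified likelihood ratio test, and the plan says nothing to exclude it.

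The second reply is that the direction depends on a quantity not yet measured in this trial. This also stands. At a ratio of 0.25 the planned test, at 4.9-5.1%, is closer to nominal than Satterthwaite (4.4-4.5%) or Kenward-Roger (3.8-4.0%). The evidence for a higher ratio is two SEs rounded to one decimal, from a study of which 9.1 c says "While these test setups have always the talker in front", whereas this trial places the talker at the side and behind. Against that, 9.1 a itself justifies random slopes by supposing that effects differ between subjects, and even the lowest ratio that rounding allows gives about 5.8%.

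A reader might infer more than the documents support:

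- That the primary test will certainly run at 5.9%. It will not if the effect hardly varies between participants, or if another reference is used.
- That a positive primary result could not be trusted. Only results in a narrow band around p = 0.05 are affected. At the reference study's 3.0 dB the choice would not matter.
- That listening effort in c) has the same excess. The documents give no ACALES variance, so any excess there is unquantified.

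**Conclusion.** The concern holds as a minor, conditional point. The primary p-value is not fully specified. In its ordinary form (ML, chi-square) the test has a size of about 5.9% at n = 20 and 5.8% at n = 22 when the slope variance is at least about equal to the error variance of a participant's mean difference. It is about 5% at a ratio of 0.25 and about 4% at zero. The plan's own SEs favour the first case, subject to their rounding and to the different talker position. The closed form also assumes balanced data under 9.3.7. The adjacent-room analysis in f) has a similar or slightly larger excess without the slope condition.

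**What to change.** In 9.3.2 b) and c), replace the likelihood ratio sentence with: *P-values for fixed effects will come from F or t tests on the REML fit with Satterthwaite degrees of freedom, with 95% confidence intervals from the same method.* Kenward-Roger is an acceptable alternative, as is a likelihood ratio test with a parametric-bootstrap reference; name one. Apply the same small-sample reference to the likelihood ratio test in f), and keep its Bonferroni correction. Use the chosen test in the 9.1 d power simulation.

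At n = 20 the Satterthwaite test has a simulated size of about 5.0% at ratios of 1 and above (approximated where the slope variance is estimated at zero).

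The cost is a sentence in three places and a rerun of the simulation; the documents do not show whether the planned simulation function supports the new test. Power for 1.0 dB falls by about 2 to 3 points under assumed SEs:

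| n | SE | Chi-square LRT | t reference |
|---|---|---|---|
| 20 | 0.35 | 79.8% | 77.3% |
| 20 | 0.374 | 74.5% | 71.8% |
| 20 | 0.40 | 69.0% | 66.0% |
| 22 | variances behind 0.374 | 78.5% | 76.2% |

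If the beamformer effect hardly varies between participants, the new test is somewhat conservative: at ratio 0 and n = 20, with correlated intercept and slope, 3.6% for Satterthwaite and 2.9% for Kenward-Roger, against 4.0% for the planned test.

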(1) to evaluate whether I-BF provides better SRTs in noisy situation with speech from side and behind than with the R-BF with hearing impaired listeners (moderate to severe hearing loss) during a lab test session. Expected SRT improvement based on previous data is about 1 dB SNR with the I-BF and SRTs are measured with the OLSA test. Tested null hypothesis: there is no difference between the RBF and the I-BF.

Secondary objective for the beamformer benefit part is

(2) to evaluate whether I-BF provides less listening effort in noisy situation with speech from side and behind than with the R-BF with hearing impaired listeners (moderate to severe hearing loss) during a lab test session. Tested null hypothesis: there is no difference between the R-BF and the I-BF measured with the ACALES test with varying SNR.

Secondary objectives for the Speech Enhancer benefit part are:

(3) to evaluate whether the investigational device with Speech Enhancer activated provides less listening effort than without speech enhancer for distant speech in a quiet listening situation for people with moderate to severe hearing loss. Tested null hypothesis: there is no difference between Speech Enhancer activated or not measured with the ACALES test with varying distance.

(4-a) to evaluate whether the investigational device with Speech enhancer activated provides better speech intelligibility than without speech enhancer for distant speech in a quiet situation for people

with moderate to severe hearing loss. Tested null hypothesis: there is no difference between Speech Enhancer activated or not measured with the WaKo Rhyme Test.

(4-b) to evaluate whether the investigational device with Speech enhancer activated provides better speech intelligibility than without speech enhancer for speech from an adjacent room in a quiet situation for people with moderate to severe hearing loss. Tested null hypothesis: there is no difference between Speech Enhancer activated or not measured with the WaKo Rhyme Test.

(5-a) to evaluate whether the investigational device with Speech enhancer activated provides better subjective speech intelligibility and less listening effort than without speech enhancer for distant speech in a quiet situation without access to visual cues for people with moderate to severe hearing loss. Tested null hypothesis: there is no difference between Speech Enhancer activated or not with the subjective assessment questionnaire.

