To determine listening effort in different situations, speech stimuli are presented in different conditions. The listening effort is subjectively rated on a predefined on a 13-point categorical scale (Luts et al, 2010) with varying difficulties (SNRs or talker distance). As speech stimuli the OLSA sentences are either presented at different levels in a background noise with fixed level or at different distances from the listener in a quiet environment. This creates different SNRs (speech levels at the position of the listener), which can be predefined or automatically adapted by the ACALES procedure (Krueger et al., 2017). ACALES adaptively chooses the SNRs or talker distances for each presentation on the basis of previous ratings. The procedure is rapid and easy to administer, resolves differences between individuals and masker conditions, and offers a high test-retest reliability (Krueger et al., 2017). Following data are provided by the ACALES procedure:

For the beamformer benefit part: for each subject the result is a two-slope curve that provides the SNR for following effort scale categorical units (ESCU) "no effort" (1), moderate effort (7), and "extreme effort" (13). The ACALES test will be repeated in 8 times: 2 test conditions (RBF and I-BF) by

two talker locations (speech from the side and speech from the back) by two test sessions (test at visit 1 and retest at visit 2).

For the Speech Enhancer part: for each subject the results are the different effort scale categorical units (ESCU) from 1= “no effort” to 13 = “extreme effort” determined at 2m, 4m and 8m. The ACALES test will be repeated in 6 times: 2 test conditions (Speech Enhancer ON and OFF) by three talker distances (2m, 4m, 8m) in just one test session.

3) WaKo Rhyme Test : speech intelligibility

The measure of the speech perception in % is an alternative procedure to evaluate the speech intelligibility in different listening conditions. The Speech perception is defined as % correct words out of a word list of 72 words. Initially an individual presentation level is measured using adaptive procedure to determine the level necessary to understand 50% of all presented words. Afterwards the correct word score can be obtained using this individual presentation level (reduced by 1 dB) by calculating the ratio of correct words by the number of total words.

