The listening effort is measured in dB SNR for three effort rating: no effort (1), moderate effort (7), and extreme effort (13). Lower SNRs indicate that the participant can tolerate more noise for the same subjective rating and stand therefore for better results. The ACALES results are measured with 2 talker locations, 2 beamformer settings, and twice (test-retest). Listening effort will be analyzed with a linear mixed effect model with sequence (test-retest), talker location, beamformer, and rated effort as fixed effects. Participants will be treated as random factor with beamformer as random

slope. The fixed effects are sum coded to get estimate of talker position and beamformer that are easily interpreted. The distribution of residuals will be visually checked to be independent and identically distributed. A likelihood ratio test will be made to obtain a p-value for each fixed effect.

d) Secondary outcome: listening effort for SE benefit

The ACALES will be repeated for 3 distances and 2 conditions (SE Off vs On). The outcome is a rating on a 13 points scale, as the difficulty is fixed by the distance now. The outcome is discrete and bounded at both ends so that a non-parametric test should be applied. Wilcoxon signed rank test will be made for each distance and Bonferroni correction for multiple comparison will be made for the three distances.

e) Secondary outcome: speech test for SE benefit

Word recognition is measured in percent for 2 conditions (SE Off vs On) and in two independent setups: 4 m distance and talker in adjacent room. Percent scores will be converted to arcsin units (Sherbecoe & Studebaker, 2004) for variance normalization. A paired t-test will be made for each condition, as the test setups address different and unrelated listening conditions.

f) Secondary outcome: subjective assessment questionnaire.

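### The ACALES beamformer model has no term for the run or for person-by-effort differences, so its talker-location and visit p-values are unreliable, and it cannot say at which effort level a beamformer benefit arises

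*Combined protocol and SAP*

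**What the plan says.** Objective 2 (section 2) tests one null hypothesis: "there is no difference between the R-BF and the I-BF measured with the ACALES test with varying SNR". It names no effort level.

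Section 6, item 2 describes the data: "for each subject the result is a two-slope curve that provides the SNR for following effort scale categorical units (ESCU"), at ratings 1, 7 and 13. It continues: "The ACALES test will be repeated in 8 times: 2 test conditions (RBF and I-BF) by" two talker locations by two visits.

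Section 9.3.2 c gives the model: "Listening effort will be analyzed with a linear mixed effect model with sequence (test-retest), talker location, beamformer, and rated effort as fixed effects". For the random part: "Participants will be treated as random factor with beamformer as random" slope. It then says: "The distribution of residuals will be visually checked to be independent and identically distributed", and "A likelihood ratio test will be made to obtain a p-value for each fixed effect". Tests are two-sided at 0.05.

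The model has no random effect for the run, none for participant-by-rated-effort, and no beamformer-by-rated-effort interaction. The primary SRT model in 9.3.2 b does carry an interaction (location by beamformer), and 9.3.2 d tests Speech Enhancer effort separately at each distance.

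**The concern.** Three points read from one fitted curve share that run's error. If a run is shifted by chance, all three SNRs shift together. People may also differ, stably, in how many dB separate effortless from extremely effortful listening. The participant intercept and beamformer slope capture neither source, so both land in the residual.

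They act in opposite directions. Shared run error makes the tests of talker location and visit too liberal, because 24 rows are counted where there are 8 runs. Spread differences enlarge the residual without adding error to a location or visit contrast, so they make those tests too conservative. The plan promises a p-value for each of these effects, and its only safeguard is a visual residual check with no stated fallback.

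Separately, one common beamformer shift is fitted to all three effort levels. At stake is whether the reader can learn if I-BF helps in easy, moderate or hard listening.

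**Working it through.** **Plan's own figure.** None exists for ACALES: no variance, effect size or power is given. The sample size rests on the SRT endpoint (20 participants, 80% power, 1.0 dB; 20 × 1.10 = 22). That power came from simulation on individual data not in the documents, so it cannot be reproduced. Nothing below depends on it.

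**Inputs from the documents.** 8 runs and 3 SNRs per run, so 24 rows per participant; fixed and random effects as in 9.3.2 c; two-sided 0.05; likelihood ratio tests.

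**Assumed inputs.** n = 20; shared run SD 1.0 dB; run-to-run noise in curve tilt SD 0.5 (effort coded −1, 0, +1); point noise SD 0.5 dB; SD between people of the 1-to-13 spread, S, from 0 to 8 dB; SD between people of the true beamformer effect, τ, from 0.5 to 1.5 dB.

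**Location and visit.** The true variance of one person's location difference is 2 × (1.0²/4 + 0.5²/12) = 0.542. The model uses 2 × s²/12 = s²/6. After intercept and slope, 22 degrees of freedom per person feed s²:

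- 6 between runs, each 3 × 1.0² + 0.5² = 3.25, total 19.5
- 8 for tilt, each 2 × (S²/4 + 0.5²) + 0.5² = S²/2 + 0.75, total 4S² + 6
- 8 for curvature, each 0.25, total 2

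So s² is about (27.5 + 4S²)/22, and the size is about 2 × [1 − Φ(1.96/√ratio)], where ratio = 0.542/(s²/6).

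| Spread SD S (dB) | s² | s²/6 | Ratio | Approx. size | Simulated size |
|---|---|---|---|---|---|
| 0 | 1.25 | 0.208 | 2.60 | 22% | 23% |
| 2 | 1.98 | 0.330 | 1.64 | 13% | 13% |
| 4 | 4.16 | 0.693 | 0.78 | 2.7% | 3.5% |
| 6 | 7.80 | 1.299 | 0.42 | 0.2% | 0.6% |
| 8 | 12.89 | 2.148 | 0.25 | 0.01% | 0.1% |

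The simulation (8,000 trials per setting) fits the planned model by maximum likelihood. The approximation ignores sampling variation in s².

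The same liberal bias appears if the dependence is expressed as a within-run correlation r with no spread differences. The ratio is then (1 + 2r)/((22 − 4r)/22): 1.69, 2.20, 2.75 and 3.35 at r = 0.3, 0.5, 0.7 and 0.9, giving sizes of 13%, 19%, 24% and 28%.

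**Beamformer.** Here the random slope can absorb shared run error. The true variance of one person's beamformer difference is τ² + 0.542; the model fits slope variance + s²/6. The fit is adequate while s²/6 is below the true variance. Otherwise the slope variance is estimated at zero and the model variance is too large.

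- τ = 0.5: true variance 0.792, against s²/6 of 0.693, 1.299 and 2.148 at S = 4, 6 and 8. The random-effects covariance is on its boundary in 46%, 90% and 99% of simulated trials. Size is 4.9%, about 2% and about 0.5% (5.5% and 6.3% at S = 0 and 2).
- τ = 1.0: true variance 1.542, exceeded only at S = 8.
- τ = 1.5: true variance 2.792, not exceeded even at S = 8.

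Power of the planned test, against a paired t-test on participant means:

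| τ (dB) | S (dB) | True effect (dB) | Planned | Paired t |
|---|---|---|---|---|
| 0.5 | 6 | 1.0 | 99.5% | 99.8% |
| 0.5 | 8 | 1.0 | 96% | 99.8% |
| 1.0 | 8 | 1.0 | 90% | 93% |
| 1.5 | 8 | 1.0 | 74% | 72% |
| 0.5 | 6 | 0.59 | 67% | 80% |
| 0.5 | 8 | 0.59 | 46% | 80% |

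**Effort levels.** A benefit of 1 dB at one level only enters the beamformer effect as 1/3 = 0.33 dB. With n = 22, residual SD 1.0 to 2.5 dB, τ 0.5 to 1.0 dB and r of 0.3 or 0.7, power is 14% to 57%, against 73% to 100% for 1 dB at all levels. Equal and opposite effects at ratings 1 and 13 average to zero; rejection was then 5% to 8%, close to the nominal rate.

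**The case against.** The strongest reply is that objective 2 has one hypothesis, the beamformer difference, and that this test is largely protected. That stands. The rows are not treated as plainly independent, only as independent given each person's intercept and slope. With shared run error alone (r from 0.3 to 0.9, n = 22) the beamformer test rejects 5.5% to 6.4% of the time. Location and visit carry no hypothesis in section 2.

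The setting that harms the beamformer test is also not the one the documents point to. Their only anchor is the reference SRT study: a device-effect SE of 0.4 dB in 20 users. Read as the SE of the full difference, it implies a per-person SD of 0.4 × √20 = 1.79 dB. The assumed τ of 0.5, 1.0 and 1.5 give √(τ² + 0.542) = 0.89, 1.24 and 1.67 dB. The nearest is τ = 1.5, where the test is sound. This anchor is SRT rather than ACALES, and spread SDs of 6 and 8 dB have no source in the documents.

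A reader might infer that the objective 2 p-value is itself wrong. The documents do not support that as a general statement. The drop from 80% to 46% needs a true effect near 0.59 dB, whereas the smallest effect of interest in 9.1 (set for SRT) is 1 dB.

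A reader might also infer that a benefit at one effort level cannot be seen. It can: with residual SD 1.5 dB, τ 0.5 and r 0.5, a single-level benefit of 2 dB had 87% power and one of 3 dB had 99%. What is missing is its attribution to a level. Because objective 2 names no level, testing the average shift is a legitimate choice.

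What survives is that 9.3.2 c undertakes to report p-values for location and visit, and nothing in the model makes those reliable.

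**Conclusion.** The point holds in a limited form. The location and visit p-values planned for ACALES are unreliable, and the direction of the error depends on variances that the documents do not give: about 23% false positives with shared run error alone, under 1% at a spread SD of 6 to 8 dB.

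The beamformer test is close to nominal in most settings. It becomes clearly conservative only if the spread SD is about 6 dB or more and the beamformer effect varies little between people (SD about 0.5 dB), with a milder loss at SD 1.0 and spread SD 8. At a 1 dB effect the loss is at most about 5 points in the settings examined.

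The missing beamformer-by-effort term needs no variance assumption: a single-level effect is divided by three, opposite end effects cancel, and no level-specific result is planned.

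The magnitudes rest on the assumed SDs and on complete, balanced data. The primary SRT analysis is not affected. This is worth correcting before analysis, but it does not undermine the study.

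**What to change.** In 9.3.2 c:

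1. State that objective 2 concerns the average shift over the three ratings. Test beamformer, location and visit on one value per run, the mean of the three SNRs, with the random structure of the primary model. Alternatively, keep the rows and add random effects for participant-by-rated-effort and for run (participant by beamformer by location by visit).
2. As a separate supportive analysis, fit the row-level model with those two random effects, rated effort as a 3-level factor and a beamformer-by-rated-effort interaction. Report I-BF minus R-BF at 1, 7 and 13 with confidence intervals. Label these supportive, or apply Bonferroni as in 9.3.2 d and f.

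The two steps must stay separate, because the interaction cannot be fitted to per-run means. Nor should the interaction be added without the random effects: with no run term, its test had size 1.4% to 2.4% at r = 0.3 and 0.1% or less at r = 0.7.

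The cost is SAP wording and a few lines of R, with no new data. With complete balanced data the average beamformer estimate does not change. The downside is two extra variance terms in the row-level model.
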